#### 5.4.3. Concomitant Medications

Prior and concomitant medications will be coded using the World Health Organization (WHO) dictionary version September 2017. Prior and concomitant medications will be presented in a data listing, and concomitant medications will be summarized by treatment group.

#### 5.4.4. Assessment of Vital Signs

Descriptive summaries of vital signs data including oral or aural temperature, respiratory rate, pulse, and blood pressure (systolic and diastolic) and respective changes from Baseline, will be presented by time point and treatment group. Three consecutive blood pressure and pulse readings are recorded at each assessment time point and all blood pressure and pulse analyses will be based on the average of triplicate measurements.

The number and percentage of patients with any PCS vital sign occurring post-Baseline will also be summarized by time point and treatment group (Table 5). All vital signs will be listed with PCS vital signs flagged.

Table 5 Criteria for Potentially Clinically Significant Vital Signs

Parameter	Flag	Criteria Observed Value
Contain his advances (months)	High	≥ 150
Systolic blood pressure (mmHg)	Low	≤ 90
Diastolic blood pressure (mmHg)	High	≥ 100
Diastone blood pressure (mining)	Low	≤ 50
Hand water/Data and a (larger)	High	≥ 110
Heart rate/Pulse rate (bpm)	Low	≤ 50
Tomporatura (9C)	High	≥ 38
Temperature (°C)	Low	< 35

#### 5.4.5. ECG Assessments

ECG measurements will be provided by a central reader.

ECGs are recorded in triplicate one minute apart, and all ECG analyses will be based on the average of triplicate measurements. The mean of the 3 triplicates (9 assessments) performed on Day -1 will be used as the Baseline for all analyses of that safety parameter.

ECG variables and their change from Baseline will be summarized with descriptive statistics by time point and treatment group. ECG variables will include heart rate, PR interval, RR interval, QRS interval, QT interval, and QTc interval corrected for heart rate using Fridericia's correction, QTcF.

QTcF values will also be tabulated for their absolute values and tabulated relative to Baseline measurements in order to detect individual QTcF changes. Additionally, the number and percentage of patients who meet the PCS values defined in Table 6 will be summarized.

Table 6 Criteria for Potentially Clinically Significant ECG Parameters

			Criteria
Parameter	Flag Observed Value		Change from Baseline or Observed Value
Heart Data (hous)	High	> 110	
Heart Rate (bpm)	Low	≤ 50	
QTcF a Interval (msec)	High Male	> 450	>30-60, > 60, > 450-480,
Q'Tel' Interval (insee)	High Female	> 470	> 480-500, > 500
QRS Interval (msec)	High	> 120	
PR Interval (msec)	High	> 220	

<sup>a QTc interval is derived as: QTcF=QT Interval (msec) / (RR (msec)/1000)(1/3)

To understand the effect of treatment arm on the change in QTcF, an ANCOVA will be performed by assessment times (visit and timepoint within visit) using the change from Baseline (as dependent variable) with treatment arm (MIN-101 32 mg, MIN-101 64 mg, and placebo) as a factor, and Baseline value as covariate. Estimates for the difference at each assessment time for each dose group versus placebo, standard error of the mean, and the upper bound of the 2-sided 90% confidence intervals will be presented.

Important abnormalities in ECG waveform that are changes from Baseline readings will also be reported in a listing, as well as PCS ECG parameters.

#### 5.4.6. Physical Exams

Physical examinations will be listed by treatment group. Anthropomorphic measurements (height, weight, BMI, and waist circumference) will be summarized by treatment group and listed within the Vital Signs presentations.

#### 5.4.7. Assessment Tools

- Abnormal Involuntary Movement Scale (AIMS): AIMS is rating scale that was designed to measure tardive dyskinesia (TD).
  - O Scoring: The AIMS scale has 14 items that are rated from 0 (none) to 4 (severe). The analysis will be limited to items 1-10. A composite movement score will be derived as the sum of scores across items 1-7 of the AIMS categories I (orofacial movements), II (extremity and truncal dyskinesia), and III (global severity and distress).
  - O Analysis: The observed composite movement score and Overall severity index [item 8, severity of abnormal movements overall), incapacitation (item 9) and patient awareness (item 10)] and changes from Baseline will be summarized by treatment group and study visit. Complete data will be presented in patient data listings by treatment group and visit.
- Barnes Akathisia Rating Scale (BARS) is a multiple-choice questionnaire to provide an assessment of akathisia, a state of motor restlessness.
  - O Scoring: The BARS scale has 3 items that are rated from 0 (absence/no distress) to 3 (most severe) and one global assessment rated from 1 to 5. The BARS rating scale is scored by summing the scales for Objective Akathisia, Subjective Awareness of Restlessness and Subjective Distress Related to Restlessness yielding a total score ranging from 0 to 9. An additional Global Clinical Assessment of Akathisia uses a 5-point scale ranging from 0 4.
  - Analysis: The BARS score and Global Clinical Assessment of Akathisia and change from Baseline will be summarized by treatment group and study visit.
     Complete data will be presented in patient data listings by treatment group and visit.
- Simpson-Angus Scale (S-AS): The S-AS measures drug-induced extrapyramidal syndromes.
  - Scoring: The S-AS is the sum of 10 items rated from 0 (normal/not present) to 4 (severe stiffness/rigidity). As such, the range of scores is 0 to 40, with increased scores indicate increased severity.
  - Analysis: The S-AS score and change from Baseline will be summarized by treatment group and study visit. Complete data will be presented in patient data listings by treatment group and visit.
- Sheehan Suicidality Tracking Scale (STS): This is a prospective rating scale that tracks treatment-emergent suicidal ideation and behaviors.

- O Scoring: Each item is scored on a 5-point Likert scale from 0 (not at all) to 4 (extremely). Data from the STS can be analyzed as individual item scores, a subscore for suicidal ideation (sum of scores from items 2, 3, and 4, plus score from item 5 if ≤ 1), a subscore for suicidal behavior (sum of scores from items 6, 7, and 8, plus score from item 5 if > 1) and the total scale score (calculated by add scores from Questions 1a (only if 1b is coded YES), + 2 through 11 + [the highest of 12 or any row of 16] + [the highest of 14 or any row of 15] + 17 + 20.
- Analysis: The two subscores and total scale score and change from Baseline will be summarized by treatment group and study visit. Complete data will be presented in patient data listings by treatment group and visit.
- The Readiness for Discharge Questionnaire (RDQ), assessed at hospital discharge after the
  initial dosing phase of the double-blind and open-label extension phases, will be presented in
  a listing by treatment and visit.

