See Attachment 4 for an example of the BARS.

**Simpson-Angus Scale (SAS)** is an established reliable and valid rating scale that measures drug-induced extrapyramidal syndromes using 10 items rated from 0= not present to 4 = extremely severe (Simpson & Angus 1970). It consists of one item measuring gait (hypokinesia), six items measuring rigidity (arm dropping, shoulder shacking, elbow rigidity, wrist rigidity, leg pendulousness, and head dropping) and three items measuring glabella tap, tremor and salivation. As such, the range of scores is 0 to 40, with increased scores indicate increased severity.

See Attachment 12 for an example of the SAS.

Sheehan Suicidality Tracking Scale (Sheehan-STS) is a prospective rating scale that tracks both treatment-emergent suicidal ideation and behaviors will be performed at the times specified in the Time and Events Schedules. The Sheehan-STS is a scale that can be administered by the clinician or the patient through self-report. Each item is scored on a 5-point Likert scale (0 = not at all, 1 = a little, 2 = moderately, 3 = very, and 4 = extremely). Data from the Sheehan-STS can be analyzed as individual item scores, and total score (calculated by add scores from Questions 1a (only if 1b is coded YES), + 2 through 11 + [the highest of 12 or any row of 16] + [the highest of 14 or any row of 15] + 17 + 20. The Sheehan-STS was adapted from the Suicidality Module of the MINI Structured Diagnostic Interview for DSM-5 (Coric et al. 2009).

See Attachment 11 for an example of this scale.

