# 10.8.6.1. Sheehan Suicidality Tracking Scale

On the basis of the data collected using the Sheehan-STS, potential suicide-related events will be categorized by the investigator using the event report (page 2 of the scale).

Descriptive statistics of score values and changes from Baseline will be summarized at each scheduled time point. The endpoint of interest will be the proportion of patients with a suicide-related outcome.

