#### ATTACHMENT 11: SHEEHAN SUICIDALITY TRACKING SCALE

#### SHEEHAN-SUICIDALITY TRACKING SCALE (S-STS)

1	did you have any accident? (this includes taking too much of your medication accidentally) IF NO, SKIP TO QUESTION 2. IF YES, GO TO QUESTION 1a:		NO 🗆	•	YES 🗆	
la.	how seriously did you plan or intend to hurt yourself in any accident, either by not avoiding a risk or by causing the accident on purpose? IF THE ANSWER TO QUESTION 1a IS 0 (= Not at all), SKIP TO QUESTION 2. IF THE SCORE IS 1 OR HIGHER, GO TO QUESTION 1b:	Not at all	A little	Moderately 2	Very 3	Extremely 4
1b.	did you intend to die as a result of any accident?		NO 🗆		YES 🗆	
Sinc	e your last visit, how seriously did you:	Not at all	Alittie	Moderately	Very	Extremely
2.	think (even momentarily) that you would be better off dead, need to be dead or wish you were dead? How many times?	0	1	2	3	4
3.	think (even momentarily) about harming or hurting or injuring yourself – with at least some intent or awareness that you might die as a result – or think about suicide (killing yourself)? How many times?	0	1	2	3	4
4	have a voice or voices telling you to kill yourself or have dreams with any suicidal content? mark either or both:a voice or voicesa dream	0	1	2	3	4
5.	have any suicide method in mind (i.e. how)? #	0	1	2	3	4
6.	have any suicide means in mind (i.e. with what)? #	0	1	2	3	4
7.	have any place in mind to attempt suicide (i.e. where)? * #	0	1	2	3	4
8.	have any date / timeframe in mind to attempt suicide (i.e. when)?*#	0	1	2	3	4
9.	intend to act on thoughts of killing yourself? mark either or both: did you intend to act: at the time at some time in the future	0	1	2	3	4
10.	intend to die as a result of a suicidal act? mark either or both: did you intend to die: at the time at some time in the future	0	1	2	3	4
11.	feel the need or impulse to kill yourself or to plan to kill yourself sooner rather than later? mark either or both: was this: to kill yourself to plan to kill yourself mark either or both: was this: largely unprovoked provoked	0	1	2	3	4
12.	take active steps to prepare for a suicide attempt in which you expected or intended to die (include anything done or purposely not done that put you closer to making a suicide attempt)?	0	1	2	3	4
13.	injure yourself on purpose without intending to kill yourself? How many times?	0	1	2	3	4
14.	attempt suicide (try to kill yourself)?	0	1	2	3	4

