"A s	uicide attempt is a potentially self-injurious behavior, associated with at least some intent (> 0) t	to die as a re	sult of the	act. Evidence t	hat the ind	Widual

"A suicce attempt is a potentially self-injurious behavior, associated with at least some intent (>-0) to die as a result of the act. Evidence that the individual intended to kill him- or herself, at least to some degree, can be explicit or inferred from the behavior or circumstance. A suicide attempt may or may not result in actual injury." (FDA 2012 definition). \* Note: items 7 & 8 on 5-STS ("a plan for suicide") means not going beyond ideas or talking about a plan for suicide. If actual behaviors occurred, the event should not be coded on item 7 or 8, but as "preparatory behavior" (item 12). Both events can occur separately over the same timeframe. # Note: clinician should ask for details.

Copyright Sheehan DV 2005-2017. All rights reserved. Permissions:[contact]

Page 1 of 3

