### FOR CLINICIAN USE ONLY

17. Missed appointm	ent - reason: subject died from a completed suicide?	0	100
18. Missed appointm	ent - reason: subject died, but not enough information to code as a suicide?	0	0
19. Missed appointm	ent - reason: subject died from cause(s) other than suicide?	0	0
20. Missed appointm	ent - reason: subject alive, but not available because of a suicide attempt?	0	4
21. Missed appointm	ent - reason: subject alive, but not available for known reasons other than suicide?	0	0
22. Missed appointm	ent - reason: subject alive, but not available, for uncertain reasons, or "lost to follow up"?	0	0
Total Scale Score	Add scores from Questions 1a (only if 1b is coded YES), + 2 through 11 + [the highest of 12 or any row of 16] + [the highest of 14 or any row of 15] + 17 + 20 [on page 3].		

I have reviewed the answers on Pages 1 and 2 with the patient.

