Table	14.3.5.2.2	Vital Signs Parameter Shifts from Baseline	Safety
Table	14.3.5.3.1.1	ECG Parameters and Change from Baseline by Time Point	Safety
Table	14.3.5.3.1.2	ECG Parameters and Change from Baseline by Time Point, 01 February 2020 Cutoff	Safety
Table	14.3.5.3.2.1	QTcF (msec) Values and Change from Baseline Relative to Predefined Thresholds of Clinical Significance	Safety
Table	14.3.5.3.2.2	QTcF (msec) Values and Change from Baseline Relative to Predefined Thresholds of Clinical Significance, 01 February 2020 Cutoff	Safety
Table	14.3.5.3.3.1	Effect of Treatment Arm on Changes in QTcF using ANCOVA	Safety
Table	14.3.5.3.3.2	Effect of Treatment Arm on Changes in QTcF using ANCOVA, 01 February 2020 Cutoff	Safety
Table	14.3.5.3.4.1	Patients with Clinically Significant ECG Abnormalities Occurring Post-Baseline	Safety
Table	14.3.5.3.4.2	Patients with Clinically Significant ECG Abnormalities Occurring Post-Baseline, 01 February 2020 Cutoff	Safety
Table	14.3.5.3.5.1	Patients with Potentially Clinically Significant ECG Abnormalities Occurring Post-Baseline	Safety
Table	14.3.5.3.5.2	Patients with Potentially Clinically Significant ECG Abnormalities Occurring Post-Baseline, 01 February 2020 Cutoff	Safety
Table	14.3.5.3.5.3	ECG Parameter Shifts from Baseline	Safety

T. 1.1		Description	Population
Table	14.3.6.1	Summary and Change from Baseline in Abnormal Involuntary Movement Scale (AIMS) Composite Movement Score and Severity Index, by Visit	Safety
Table	14.3.6.2	Summary and Change from Baseline in Barnes Akathisia Rations Scale (BARS) and Global Clinical Assessment of Akathisia, by Visit	Safety
Table	14.3.6.3	Summary and Change from Baseline in Simpson- Angus Scale (S-AS) Score, by Visit	Safety
Table	14.3.6.4	Summary and Change from Baseline in Sheehan Suicidality Tracking Scale (STS) Subscores and Total Scale Score, by Visit	Safety
Listings	•		•
Listing	16.2.1	Patient Disposition	Enrolled
Listing	16.2.2.1	Protocol Deviations	ITT
Listing	16.2.2.2	Inclusion/Exclusion Criteria	Enrolled
Listing	16.2.3	Inclusion in Analysis Populations	Enrolled
Listing	16.2.4.1	Demographic and Baseline Characteristics	ITT
Listing	16.2.4.2	Psychiatric and Medical History	ITT
Listing	16.2.4.3	Schizophrenia Characteristics at Baseline	ITT
Listing	16.2.4.4	CYP2D6 Genotyping	Enrolled
Listing	16.2.4.5	Concomitant Medication Blood Sampling	Enrolled
Listing	16.2.4.6	Urine Drug and Alcohol Screening	Enrolled
Listing	16.2.4.7	Hospital Admissions and Discharge/Continuation	ITT

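### The SAP's Sheehan-STS suicidal behavior subscore is built from planning-thought items and gives no weight to preparation, attempts or completed suicide

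*SAP*

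**What the plan says.** SAP 5.4.7 (Assessment Tools) derives three summary scores from the Sheehan-STS:

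- **Ideation subscore:** items 2 + 3 + 4, plus item 5 if it is 1 or less.
- **Behavior subscore:** the "subscore for suicidal behavior (sum of scores from items 6, 7, and 8", plus item 5 if it is above 1.
- **Total score:** a formula that agrees with the one printed on the scale in Protocol Attachment 11, which begins "Add scores from Questions 1a (only if 1b is coded YES), + 2 through 11".

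All three, with change from Baseline, are to be summarized by treatment group and visit. The only STS table in the SAP 9.1 list is 14.3.6.4, for "Suicidality Tracking Scale (STS) Subscores and Total Scale Score, by Visit". The same table is re-run for the extension phase in SAP 9.2.

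The protocol is different. Section 8.4 says: "Data from the Sheehan-STS can be analyzed as individual item scores, and total score". It mentions no subscores, and Attachment 11 defines none. Protocol 10.8.6.1 states that "potential suicide-related events will be categorized by the investigator using the event report (page 2 of the scale"), and then: "The endpoint of interest will be the proportion of patients with a suicide-related outcome".

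**The concern.** The subscore's label does not match its content. Item 6, for example, asks whether the patient did "have any suicide means in mind (i.e. with what"). Items 5, 7 and 8 ask the same about method, place and date. For items 7 and 8 the scale is explicit: "If actual behaviors occurred, the event should not be coded on item 7 or 8"; such an event belongs on item 12. So on those two items the SAP reports as behavior what the scale says is not behavior, and it leaves out every item that does record behavior.

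Table 14.3.6.4 would therefore be the only by-arm STS result labelled suicidal behavior, and it could point the wrong way. An arm with attempts could show zero while an arm with planning thoughts shows an increase. This matters in a trial that withdraws prior psychotropic medication and assigns one third of patients to placebo for 12 weeks.

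The missing endpoint is a separate matter. The protocol chose a proportion of patients, which is the natural summary for rare events, and the SAP replaces it with mean scores.

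**Working it through.** There is no planned figure to reproduce. The check maps the SAP formulas onto the items in Attachment 11 and scores test profiles.

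**Item content (Attachment 11)**

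- 5, 6, 7, 8: method, means, place, date in mind
- 9, 10, 11: intent to act, intent to die, impulse
- 12 and rows of 16: preparation
- 14 and rows of 15: attempt
- 17: completed suicide (0 or 100)
- 20: unavailable because of an attempt (0 or 4)

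**Formulas (SAP 5.4.7)**

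- Ideation = i2 + i3 + i4 + (i5 if i5 ≤ 1)
- Behavior = i6 + i7 + i8 + (i5 if i5 > 1)
- Total = i1a (only if 1b is yes) + i2 + … + i11 + max(12, 16) + max(14, 15) + i17 + i20

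The last column below is the sum of the behavioral terms already inside the SAP total: max(12, 16) + max(14, 15) + i17 + i20.

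| Profile (all other items 0) | Ideation | Behavior | Total | Behavioral terms |
|---|---|---|---|---|
| Planning thoughts only, items 5–8 = 4 | 0 | 16 | 16 | 0 |
| Preparation only, item 12 = 4 | 0 | 0 | 4 | 4 |
| Attempt only, item 14 = 4 | 0 | 0 | 4 | 4 |
| Preparation and attempt, items 12, 14 = 4 | 0 | 0 | 8 | 8 |
| Planned attempt, items 5, 6, 12, 14 = 4 | 0 | 8 | 16 | 8 |
| Completed suicide, item 17 = 100 | 0 | 0 | 100 | 100 |
| Absent because of an attempt, item 20 = 4 | 0 | 0 | 4 | 4 |
| Intent and impulse, items 9–11 = 4 | 0 | 0 | 12 | 0 |

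Four results follow.

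1. The behavior subscore reaches its maximum, 4 × 4 = 16, with no act at all. It is 0 for each act taken alone.
2. A planned attempt does score above zero, but all 8 points come from items 5 and 6 (4 + 4).
3. Items 9 to 11 enter neither subscore. The two subscores together can reach 12 + 16 = 28 of the 40 points available on items 2 to 11.
4. When item 5 rises from 1 to 2, ideation falls by 1 and behavior rises by 2, although only a thought about method has changed.

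**The missing proportion.** With the planned 167 patients per arm, one attempt rated 4 moves that arm's mean total by 4/167 = 0.024 points. A mean shift of that size would not be noticed; a count of patients would be.

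**The case against.** The strongest reply is that little depends on the subscores. They are descriptive, with no test or decision rule attached, and the events surface elsewhere. Suicidal ideation or behavior is a withdrawal criterion (Protocol 9.3), so it should appear in the discontinuation reasons by arm. Completed suicide is a listed relapse term (SAP 3.3.8). Fatal and serious adverse events are tabulated separately. Recent serious suicidal behavior is an exclusion criterion. All of this stands and limits the consequence, but it does not make the subscore correct.

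The SAP's descriptive statistics also include minimum and maximum, so the mean is not the only view of the total. Without item 17 the total cannot exceed 4 + 40 + 4 + 4 + 4 = 56, so a maximum of 100 or more would reveal a suicide. That is right for completed suicide. For attempts it fails, because a total of 4 from an attempt looks the same as 4 points of ideation.

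Protocol 8.4 says how the data can be analyzed; that is permissive and does not forbid subscores. This is fair: adding subscores is weak evidence of a deviation in itself. The fault is the content of these two.

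A behavior subscore rebuilt from the total would also be absent from Attachment 11, and it would mix 0–4 terms with a 100-point term. One suicide would move an arm mean by 100/167 = 0.60. This is a good reason to prefer deletion unless a scoring source is cited.

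Finally, the protocol does not say what counts as a suicide-related outcome, so the proportion table needs a definition first. That also stands and is reflected in the fix.

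**Conclusion.** The point holds and should be fixed. The behavior subscore in SAP 5.4.7 does not fit the scale the trial uses: it can report up to 16 points of behavior with no act, and 0 for an attempt alone or a completed suicide. The mismatch is confined to the two subscores, since the total-score formula in the same SAP sentence agrees with Attachment 11. The documents do not show where the subscore formula came from, and the conclusion does not depend on it. It assumes only that Attachment 11 is the version administered.

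For items 7 and 8 the scale's own note settles the matter; for items 5 and 6 the conclusion rests on their wording.

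Separately, the protocol's endpoint of interest for this scale is missing from SAP 5.4.7 and from the SAP's table list, and Section 7 (Changes in the Planned Analyses) does not declare it removed.

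Both points concern descriptive safety reporting. Neither affects the primary or key secondary analysis, and the underlying events are not lost.

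**What to change.** Before unblinding, do one of the following for the subscores:

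1. **Delete both.** Report the total and the individual item scores, which Protocol 8.4 names. This needs no outside scoring source and is the safer choice. An item-level summary would be an addition to the current SAP analysis.
2. **Redefine both.** Take behavior as max(12, 16) + max(14, 15) + item 17 + item 20, and remove items 5 to 8 from it. Reconcile the ideation subscore (items 5 to 11) and the placement of item 1a with Attachment 11. Cite a scoring source for both definitions, and show item 17 separately so that its 100 points do not swamp the summary.

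For the protocol endpoint, define a suicide-related outcome from the investigator's event-report categorization. Then add a by-arm table of the number and proportion of patients with one. If the sponsor does not want this analysis, list its removal in SAP Section 7.

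The cost is SAP wording, one derivation (or two deletions), one written definition and one table. The item scores and event report are part of the scale already administered; the sponsor should confirm that the event-report categorization is captured in the database.
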